### 3.5 Codebook Development

The research team will develop study codebook based on the A/TAM theory:

1. Codes will be generated from the A/TAM theory.
2. Researchers will review and revise the code in context of the data.
3. Researchers will determine the reliability of coders and the code

### 3.6 Analyses

We will complete a systematic analysis of interview transcripts to identify specific themes guided by the A/TAM to inform future implementations of the wearable device and cascading alert system. After the initial few interviews have been completed, two researchers, working independently, will use a codebook of constructs adapted from the A/TAM to identify significant phrases that exemplify each construct. They will then independently review each other’s work and come together to discuss differences of opinion and achieve consensus. The principal investigator will meet with the coders to review the codes, adding or consolidating as warranted. The researchers will then continue to perform interviews, adding codes to the codebook as needed, and meeting as a team periodically to review the codes and achieve consensus. We will use Atlas TI qualitative data analysis software to manage data and assist in analysis. Finally, we will create an overview description of the important themes, and their relationship to A/TAM constructs.

## STUDY PROCEDURES

### 4.1 Recruitment Procedure

#### 4.1.1 Patients

The participants will be recruited from Northshore University HealthSystem's Evanston Hospital, Glenbrook and Highland Park hospitals by the study team. The recruitment process will follow protocol standards to ensure consistency in the recruitment process. The participants will be informed that their participation is completely voluntary and that they can drop out at any time. The participants will also be required to sign consent forms to participate.

#### 4.1.2 Providers

Clinical team staff will be asked to participate in surveys and semi-structured interviews.

### 4.2 Inclusion and Exclusion Criteria

#### 4.2.1 Patients

##### *Ileostomy Cohort*

Inclusion Criteria:

- Patient underwent a new ileostomy formation at index hospitalization
- Patient is an inpatient at Evanston, Glenbrook, Highland Park hospitals
- Patient of Drs. [name], [name] and [name]
- At least 18 years of age
- Fluent in English
- Patient is discharging with home health services
- Patient agrees to protocol-required procedures

Exclusion Criteria:

- Patient has cognitive or physical limitations that, in the opinion of the investigator, limit the patient's ability to maintain patch/wrist device, phone
- Patient has allergy to hydrocolloid adhesives
- Patient has present skin damage preventing them from wearing a study device
- Patient discharges to a skilled nursing facility, or other subacute facilities
- Pregnancy

#### **4.2.2 Providers**

All members of the clinical care team staff will be asked to participate in the implementation of the project. We will include clinical team involved in the caring for ileostomy patients. We will recruit a total of 10 providers to participate in the semi-structured interviews.

### **4.3 Informed Consent Procedure**

#### **4.3.1 Patients**

The research coordinator is responsible for explaining the study to potential and willing participants. The consent process begins once the participant is interested in being enrolled in the study. At this time, the research coordinator will conduct a thorough review of the consent details, including study procedure, risks, confidentiality, etc. with the potential participants. Participants will be given adequate time to think about their decision to participate without coercion on the part of the researchers. Whether a patient wishes or not, to be enrolled, that patient's medical care will not be affected. No consent will be completed if the participants have unanswered questions, and potential participants may talk over the details with the consent with whomever they wish, prior to giving consent.

Participants will need to be consented in a face-to-face meeting with the research coordinator and if they wish to obtain a copy of the consent, they are free to do so. If there is a change in the consent during ongoing study activities, the participant may be asked to re-consent, if changes will have a direct effect on the participant.

The research coordinator is responsible for explaining the study to potential and willing participants or to their Legally Authorized Representative (LAR). The consent process begins once the participant is interested in being enrolled in the study. At this time, the research coordinator will conduct a thorough review of the consent details, including study procedure, risks, confidentiality, etc. with the potential participants or if applicable, with their LAR. Participants will be given adequate time to think about their decision to participate without coercion on the part of the researchers. Whether a patient wish to be enrolled, that patient's medical care will not be affected. No consent will be completed if the participants have unanswered questions, and potential participants may talk over the details with the consent with whomever they wish prior to giving consent.

Participants or when applicable, their LAR will need to consent in a face-to-face meeting with the research coordinator. If there is a change in the consent during ongoing study activities, the participant may be asked to re-consent if changes will directly affect the participant.

If the participant cannot provide informed consent but are interested in the study, their LAR can sign the form on their behalf. The research coordinator will answer all study-related questions and communicate all study details before signing the consent form. In addition, the research coordinator will file all legal documents confirming LAR's relation to the participant in the study binder.

During patient recruitment, if any of the approached eligible patients expresses interest in the study but is unwilling to participate in interviews, the research coordinator will present the no-interview consent form to patients as an alternative option. Once the no-interview group is full, patients will only be presented the consent form with interviews.

As part of the informed consent process:

1. The participant agrees to wear a total of 5 VCI VitalPatch for 7 days each adding up to 35 total days of monitoring. The research coordinator will place the VitalPatch on patients when they are still hospitalized. Our goal is to collect 30 days of post-discharge data.
2. The participant agrees to replace the VitalPatch every 7 days and to answer survey questions either daily (in the morning) or twice a day for the duration of the study in a timely fashion
3. The participant agrees to follow directions on the pinpointIQ application
4. The participant agrees to allow access to basic demographics, medical conditions, wearable and pinpointIQ platform data, other vital signs, medical care received during the hospitalization and subsequent 30 days, labs, medications, other procedures and surgeries, outcomes such as readmissions, surgical complications and mortality and clinical and nursing notes.
5. Importantly, the research coordinator will emphasize that the physiological data are not being monitored continuously with the patient. Patients should still follow the instructions given by their care team on what symptoms should be reported immediately, and how to report them.
6. Research coordinator documents informed consent process completion and files informed consent form
7. VitalPatch is placed on participant and patch is paired with phone.
8. Research coordinator teaches participant about VitalPatch, phone requirements, phone application and presents written information on wearing the devices and what is expected for the next 30 days
9. For enrolled participants who are discharged over the weekend or discharged before research staff placed devices on them, research coordinators will mail the study kit and schedule a phone call to guide and educate patients on placing the patch and operating the study phone. The questionnaires or interviews may be completed over the phone if participants did not complete them before discharge.
10. Participant agrees to complete required self-reported questionnaires and interviews if applicable.
11. Participant agrees to mail back the phone and any unused supplemental patches in a pre-paid mailer

Once the patient agrees to the study, the patient will sign the consent form the next day. We will give every patient at least 24 hours to decide whether or not they are willing to participate in the study. The

research coordinator will follow up with potential participants after 24 hours. We will scan the signed consent form into EPIC and link the patient's chart to the study.

However, starting on 4/19/2021, the research team noticed that someileostomy patients were admitted over the weekend but discharged the following Monday. For sampling purposes, we will include these patients in the study. For patients who require a phone consent, research coordinators will follow the below process:

1. Research coordinators will approach the eligible patients the day of discharge, introduce the study, and go over the consent form with patients
2. Research coordinators will provide the patient with two copies of the consent form and a pre-paid mailing envelope
3. Research coordinators will schedule a follow-up phone call with the patient for the next day
4. Research coordinators will call patients the next day and answer any remaining questions the patients and caregivers might have about the study

Suppose the patient is agreeable to participate in the study. In that case, the research coordinator will either (a) ask the patient for their email address and send a copy of the consent form to the patient's email address via part 11 compliant DocuSign. The research coordinator will review the consent form with the patient over the phone and have the patient sign via DocuSign. Research coordinators and the patient will both receive a signed copy of the consent form. Research coordinators will schedule to overnight the study kit to the patient. (b) If the patient does not have an email address, the research coordinators will ask the patient to sign the consent form they received at discharge, and mail back the consent form using the prepaid mailing envelope provided by the research team. Upon receiving the signed consent form, coordinators will overnight the study kit to the patient.

5. Once the patient receives the study kit, the coordinators will call the patient to guide them to put on the patches and pair the phone.
6. Coordinators will also complete required questionnaires and interviews over the phone with the patient

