## QUALITATIVE

### 3.1 Qualitative Research Aims

Receive provider and patient feedback on the application of wearable technology to post-discharge care to conduct a theory-driven evaluation of feasibility, usability, and effectiveness. We will address motivational and self-care issues at baseline, continuing and post-study from both providers and patients' viewpoints. 1) ascertain perceptions of telemonitoring and remote patient management of high-risk patients, of organization and effectiveness of care by providers using interviews and surveys; and 2) evaluate patient acceptance, perceptions of and satisfaction with wearable patches, with prompted requests for patient status information, and with escalation pathways for nurse navigators and physicians using interviews and survey tools.

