A timeline illustrating provider related study activities can be found in Figure 4.

[figure not shown]

Figure 4 Provider Interview Timeline

II. To evaluate patients' acceptance, perceptions of and satisfaction with wearable patches, with prompted requests for patient status information, and with escalation pathways for nurse navigators, midlevel providers and specialists.

**Patient enrollment (prior to discharge):** Following a detailed presentation of the device and study, and informed consent, researchers will administer a questionnaire to establish the participant's comfort and experience level with a wearable device and to ascertain that the participant has understood the limitations of the devices (e.g. that they provide continual but not constant, "real-time" monitoring) prior to hospital discharge. This will be followed by an in-person semi-structured interview. The interview is informed by A/TAM to establish the patient's readiness to use a wearable device as a means of monitoring their post-discharge status, including to establish any anticipated challenges in technology-mediated interaction with the care team; and finally, to identify any knowledge gaps that may need to be filled through the induction process. Paradata will be collected at the interview to assist with analysis.

**Patient progress (throughout the period of device use):** Monitoring of the patient's experience and satisfaction with the device and the study process will be combined with weekly monitoring questions focusing on the following aspects: **(a)** experience with physical use and tolerance of the device; assess any difficulty in keeping it in place, any skin reaction, possible somatization of health concerns; **(b)** experience of self-monitoring and communication with care team through the device **(c)** degree of reassurance or anxiety about the patient's recovery process; finally, **(e)** paradata from device and interaction metrics, including possible sentiment analysis of interaction text.

[figure not shown]
**Conclusion (Study endpoint):** **(a)** Surveys will be administered at study endpoint to assess each patient's strength of feeling in each response by recording not only the response itself but also the "paradata"—the researcher's assessment of the patient's affect in providing the response. On this basis, **(b)** in

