## **4.4 Semi-Structured Interview Process**

### **4.4.1 Patients**

After obtaining informed consent, the research coordinator will set up a time to complete the questionnaire and a 30-minute semi-structured interview with the patient before discharge. Patients will be asked at the time of consent if they are willing to provide an email address for reminders and updates. After 30 days of remote monitoring, the research coordinator will contact patients via phone to complete the survey.

At the study endpoint, the research team will make three phone attempts to reach the patient on different days and times. If unable to reach the patient, the patient will then be contacted by their provider to remind them of completing the survey and interview if applicable.

Before the interview starts, the researcher will remind the participant not to use their name during the interview as it will be recorded. These interviews will be transcribed and then de-identified by study staff. They will also be reminded that recording is required for participation.

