### 8.6.1 Ileostomy Pre-discharge Interview

Example of questions	Example of probing questions
What is your previous experience with using wearable devices?	
 
• If no experience, probe why
 
• Did you find it useful? How was it useful?
 
• What were some of the challenges with it?
 

What is your previous experience with telemonitoring?	
 
• If no experience, probe why
 
• How did you feel about the telemonitoring?
 
• What were some of the challenges with telemonitoring?
 

Can you describe your experiences living with XXX prior to the surgery?	
How do you manage your health conditions at home?	
 
• Is there anything you do related to diet or medications?
 
• Tell me about some of the challenges with ...
 
• Are your family/friends involved with managing your health?
 
 
How do you feel about ...

What happened leading up to this ileostomy procedure?	
 
• What physical symptoms of your illness did you experience?
 
• Who participated in the decision to go through with this procedure?
 
• What did they say?
 
• How do you feel about being in the hospital?
 

We know that managing your health condition could be very expensive.
 
Can you give us some examples of what those expense are?
 
Has that been a problem for you?
	
 
• Can you give us some examples of how you have dealt with those expenses?
 

Can you describe your initial reaction to the stoma?	
In what way, if any, do you think participating in this study might be beneficial to you?	
How do you feel about the upcoming discharge?	
Negative feelings – Why?
 
Positive feelings – Is being enrolled in the study part of the reason (of the positive feelings)? Why?

Is there anything you would like to add? Or is there anything else you would like to discuss?	

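### On the phone-consent route the baseline questionnaire and readiness interview cannot precede discharge, and the listed steps allow them to follow the start of home monitoring

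*Protocol*

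**What the plan says.** Three places in the Protocol set the timing and purpose of the patient baseline.

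- Section 3.1 names three time points: "We will address motivational and self-care issues at baseline, continuing and post-study".
- Section 3.2, in the paragraph on patient enrollment, has a questionnaire on comfort, experience and understanding of the device's limits completed "prior to hospital discharge. This will be followed by an in-person semi-structured interview". The interview is meant "to establish the patient's readiness to use a wearable device as a means of monitoring their post-discharge status", and to bring out anticipated challenges and knowledge gaps that induction can then fill.
- Section 4.4.1 has the coordinator "set up a time to complete the questionnaire and a 30-minute semi-structured interview with the patient before discharge".

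Section 4.3.1 (Patients) then describes two routes for people who leave hospital before set-up.

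- Item 9 covers patients already enrolled who go home over a weekend or before devices are placed. They are mailed a kit, and "The questionnaires or interviews may be completed over the phone if participants did not complete them before discharge".
- The phone-consent process covers patients approached on the day of discharge. They are called the next day, sign electronically or by post, and are sent the kit overnight. Step 5 is patch and pairing. Step 6 is: "Coordinators will also complete required questionnaires and interviews over the phone with the patient".

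The guide in section 8.6.1 is not adapted for either route. It still includes "How do you feel about the upcoming discharge".

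**The concern.** Readiness and anticipated challenges look forward. They are informative about acceptance if the patient answers before living with the device at home. If the interview takes place after home monitoring has begun, the answers may contain some early experience, and the analyst cannot separate the two without knowing the dates.

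The questionnaire in section 3.2 also serves as a check that the patient has grasped what the device does not do, and the interview is meant to expose gaps for induction to fill. Both lose some of their use if they come after monitoring at home has started.

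The late timing is also not spread at random. Section 4.3.1 introduced phone consent for patients admitted over a weekend and discharged on the Monday, so baseline timing is tied to the kind of stay.

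**Working it through.** There is no sample-size or power figure to reproduce here. The check compares the stated timings and counts days along the phone-consent steps.

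**Inputs from the Protocol.** Approach on the day of discharge, taken as day 0; call the next day; overnight kit after signature (electronic) or after the posted form arrives (paper); set-up call when the kit arrives; a 30-day post-discharge window; 10 patients.

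**Assumptions.** The patient signs on the day of the first call, and set-up happens on the day the kit arrives. Return post takes m days. The Protocol gives no value for m, so I use 2 to 5.

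| Route | Consent in hand | Kit arrival and step 5 | Earliest baseline in listed order | Share of 30 days elapsed |
|---|---|---|---|---|
| Standard (4.4.1) | before discharge | patch placed in hospital | before discharge | 0 |
| Phone, electronic | 0 + 1 = day 1 | 1 + 1 = day 2 | day 2 | 2/30 = 7% |
| Phone, paper | day 1 + m | day 2 + m | day 4 to 7 | 4/30 = 13% to 7/30 = 23% |

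These are lower bounds under the assumptions above. Two gaps should be kept apart:

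- *Discharge to baseline.* On the phone route this is always above zero, because consent follows discharge. That conflicts directly with sections 3.2 and 4.4.1.
- *Start of home monitoring to baseline.* In the listed order this can be zero, if steps 5 and 6 share a call. It has no upper limit, because neither step 6 nor item 9 sets a latest time.

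**If the baseline is moved to the transit period.** With electronic signature it falls between day 1 and day 2. On paper it falls between day 1 + m and day 2 + m, that is day 3 to 4 for m = 2 and day 6 to 7 for m = 5. It remains after discharge, but home device use before it is zero in each case.

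**Share of the data.** One patient is 1/10 = 10% of the cohort. The share of the interview data could be larger, because section 4.3.1 allows a no-interview consent group of unstated size. If that group counts within the 10, fewer than 10 patients are interviewed.

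**The case against.** The strongest reply is that the Protocol never requires the baseline before the patch. On the standard route the patch is placed in hospital, and the interview need only be done before discharge, so a standard patient may also be interviewed while wearing it. This stands. A reader might infer that the phone route reverses a prescribed order of baseline before exposure, but the documents contain no such rule. The supportable contrast is with discharge and the start of monitoring at home.

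Other replies also carry weight:

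- The word also in step 6 permits the same call as step 5, so appreciable experience with the device is possible but not certain.
- Item 9 is conditional. Some of those patients may have completed everything in hospital.
- A reader might infer that phone patients start monitoring unaware that it is not constant. Item 5 of the consent list has the coordinator stress exactly this, and the consent form is gone over before the kit is sent. What may come late is the check of understanding, not the information.
- A reader might infer that before-and-after comparisons of scales are spoiled. In Appendix 1 only the demographic survey and the social-support instrument are headed Pre, and neither is likely to change with a patch. The self-efficacy and stoma quality-of-life scales are headed Post there, although the contents list shows the self-efficacy scale as Pre and Post. No before-and-after test is stated.
- The prompts in section 8.6.1 are examples, and section 3.4 calls for a nondirective style. Most can still be asked at home. The one on the coming discharge cannot.

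These replies narrow the point but do not remove it. Sections 3.2 and 4.4.1 cannot be met under phone consent, and nothing in section 4.3.1 keeps the baseline ahead of home monitoring.

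**Conclusion.** The point holds in a limited form. On the phone-consent route the questionnaire and readiness interview necessarily follow discharge, by at least 2 days in the listed order. They may also follow the start of home monitoring by an interval that the Protocol does not bound. Item 9 allows the same for enrolled patients who had not completed them in hospital.

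The effect falls on the readiness interview, the comfort questionnaire and the check of understanding, all within the qualitative aim. The 30-day readmission outcome, the demographic survey and the social-support instrument are not materially affected. The day counts rest on same-day signature and set-up and, for the paper route, on an assumed 2 to 5 days of post. The overall size cannot be given, because the number of patients on these routes is not stated. The change is worth making because it is nearly free, not because the study's main result is at risk.

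**What to change.** 1. In the phone-consent steps of section 4.3.1, require the baseline questionnaire and interview after signed consent and before the patch is applied at home, for example while the kit is in transit. Apply the same condition to item 9 patients who have not yet completed them. This gives these patients what the pre-discharge rule gives standard patients: a baseline that precedes home monitoring.
2. In sections 3.2 and 4.4.1, state that on these routes this timing, by phone, replaces the in-person pre-discharge timing.
3. Record the date of the baseline relative to discharge and to the first patch.
4. In section 8.6.1, give an alternative to the prompt about the coming discharge for patients already at home.
5. When reporting the qualitative results, flag any baseline taken after device start at home.

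This needs wording changes and one recorded date, with no added patients or measures. The small downside is that set-up may wait for a 30-minute call if the interview is not done during transit.
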